Effects of ACTHAR on Advanced MRI Surrogate Markers of Disease Activity and on Comprehensive Immune Signature During MS Relapses IRB16-1390 NCT3021317 Protocol Date 10/23/19

Effects of ACTHAR on advanced MRI surrogate markers of disease activity and on comprehensive immune signature during MS relapses

This investigator-initiated trial (IST) is divided into two complementary parts:

- Advanced serial MRI studies on patients during and after an acute MS relapse. MRI will be performed at baseline, 1 month after the 1st dose of ACTHAR, and months 3, 6, and 12. ACTHAR will be administered for 10 days. Patients will start ACTHAR within 48 hours of relapse assessment.
- Serial immune assays on patients during and after an acute MS relapse. Serum and blood samples with be collected at baseline, last day of ACTHAR (day 10 of therapy), 1 month post 1st dose, and months 3 and 6.

ACTHAR will be administered by a self-injectable syringe under the skin fat tissue (subcutaneous injection). The first subcutaneous injection of ACTHAR will be done in the clinic. Subjects will undergo a teaching session with the PI ([name]) about how to give a subcutaneous injection of ACTHAR. All subsequent injections will be self-administered by the patient.

At each research visit, subjects will have a physical/neurological examination, blood pressure, height, weight, and temperature taken at the time of visits. Urine pregnancy test or urine analysis may be done if there is a clinical concern for pregnancy or urine infection. This will be based on the discretion of the investigators.

Part I. Investigational Plan-MRI

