2.6 Outcomes

This data may lead to better understanding of the mechanism of action of ACTHAR and identifying signatures/biomarkers in ACTHAR-treated MS. In addition, MRI, CD8+CD28- cell numbers, serum proteins, and RNA may be biomarkers for efficacy.

Part III. Patient criteria and publications

3.1a Inclusion Criteria

This study will be restricted to adult patients (>18 years) undergoing a clinical relapse who also must have a contrast-enhancing CNS lesion, either clinically or non-clinically relevant. Sample size under consideration is 18 patients. The population on which analyses will be conducted consists of all patients who have received at least 1 dose of study medication and for whom at least two time-points (baseline and at least one additional time-point) for MRI data are available (Intent-to-treat analysis).

3.1b Exclusion Criteria

1-Patients will be excluded if they only have a clinical relapse which is not associated with MRI findings of a new or enlarging MS lesion.

2-Patient will be excluded if they cannot give written consent

3-Patients will be excluded if they have an active infection

4-Patients will be excluded if they already received steroids (IV or oral) within last 30 days of receiving ACTHAR

5-Pregnant or lactating patients will be excluded from this study.

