3.2 Treatment failures and/or inadequate response

Patients who have not had an adequate response to the ACTH treatment after 14 days may either be given a choice of getting another round of ACTH for additional 10 days or switching to IV Methylprednisolone 1000 mg for 3 days. The scheduling of blood draws and MRIs will not be affected and continue as planed.

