3.6 Safety instructions and emergency medical contacts

All study related adverse events (AEs) and serious adverse events (SAEs) will be collected. The medical treatment for relapses is given as part of standard medical care. Hence, all AE and SAEs will be handled per standard medical practices. The emergency medical contacts will be provided to all patients.

Risks associated with the study:

The potential risks of drawing blood include a bruise at the site of the puncture. This happens rarely and inflammation of the vein and infection have been reported. Care will be taken to avoid these complications.

The research-related MRI scans are not being done for diagnostic purposes. If any abnormalities are noted during the research scans, the treating physician will be informed.

Potential risks for ACTH are listed in the package insert. Patients will receive advice on the side effects as it is done in clinical practice. The most common side effects are water gain, injection site reaction, mild insomnia, and flushing. These will be managed as per standard medical care.

The risks associated with MRI are typically claustrophobia and risks associated with contrast agents. Patient's may be given some mild sedative before the MRI. Patient's who have had prior allergic reaction to contrast agents will be excluded. Also, precontrast renal function will be assessed prior to the contrast MRI. Hydration will be recommended after the MRI.

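### Pregnancy is an exclusion, but the only stated pregnancy test is discretionary, so an unsuspected pregnancy could reach the first ACTHAR dose and the baseline research contrast MRI

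*Combined protocol and SAP*

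**What the plan says.** The opening study overview lists the examination and vital signs taken at every research visit. It then turns to pregnancy: "Urine pregnancy test or urine analysis may be done if there is a clinical concern for pregnancy or urine infection". The next sentence adds: "This will be based on the discretion of the investigators".

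Exclusion 5 in section 3.1b has no qualifier: "Pregnant or lactating patients will be excluded from this study". It names no method of verification. Section 3.1a admits adults with no limit on sex or childbearing potential, and the supplied text has no contraception requirement.

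ACTHAR starts within 48 hours of the relapse being assessed. The first injection is given in the clinic and the rest are self-administered over a 10-day course. MRI is done at baseline and at months 1, 3, 6 and 12. Section 3.6 says that "precontrast renal function will be assessed prior to the contrast MRI" and excludes patients with a previous contrast allergy. It does not mention pregnancy. The same section states "The research-related MRI scans are not being done for diagnostic purposes" and, separately, "The medical treatment for relapses is given as part of standard medical care".

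After an inadequate response, section 3.2 allows "another round of ACTH for additional 10 days" or "switching to IV Methylprednisolone 1000 mg for 3 days".

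**The concern.** The protocol treats pregnancy as a reason not to enter the study, yet its stated way of finding one works only after somebody suspects it. Early pregnancy may raise no suspicion, and that is when a routine test adds most. A site could follow the overview to the letter, record no concern, do no test, and enrol a patient whom exclusion 5 is meant to keep out.

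What is at stake is exposure to the study drug and to contrast given for research. Because the study itself orders the research contrast, the study should secure the check. The documents give no size for the fetal risk (section 3.6 refers to the package insert for drug risks), and none is claimed here.

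**Working it through.** The plan states no figure on this point, so the check is mainly a comparison of its provisions, followed by simple counts.

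**1. Is a pregnancy test required anywhere before exposure?**

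| Step | What the text requires | Pregnancy test required? |
|---|---|---|
| Eligibility (3.1b, exclusion 5) | Pregnant patients excluded | No method given |
| Each research visit (overview) | Examination, blood pressure, height, weight, temperature | Optional: needs concern, then discretion |
| Before contrast (3.6) | Renal function check, contrast-allergy exclusion | No |
| First dose (overview) | Given in clinic, with injection teaching | No |
| Retreatment (3.2) | Inadequate response after 14 days | No |

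No row would detect an unsuspected pregnancy.

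**2. Is pregnancy treated differently from the other exclusion that shares the sentence?** Active infection (exclusion 3) also has only an optional urine test. But temperature and examination are taken at every visit and can raise concern about infection. No routine visit item is aimed at early pregnancy.

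**3. Does the baseline scan use contrast?** Yes. The first specific aim in section 1.3 follows enhancing lesions seen at baseline. The Supplement plans anatomic images both before contrast and 15 minutes after it, dynamic susceptibility perfusion, and dynamic imaging for Ktrans.

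**4. What would a missed case at entry be exposed to?**
- The baseline contrast scan and 10 days of ACTHAR.
- With a second ACTH course under 3.2: 10 + 10 = 20 days.
- With the switch under 3.2: 10 days of ACTHAR plus 3 × 1000 mg = 3000 mg methylprednisolone, reading 1000 mg as the daily dose.

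**5. How many entry tests would close the gap?** One per woman of childbearing potential. Their number is not given. Over an assumed range of 6, 12 or all 18 patients, this is 6, 12 or 18 tests.

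**6. Does an entry test disturb the analysis?** The analysis population in 3.1a requires at least one dose. A positive test before dosing keeps the patient out of it, and the no-replacement rule in 3.5 concerns withdrawal after treatment. Neither is affected.

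**The case against.** **The text may be incomplete on this point.** The consent pages were removed, and the clinic or MRI unit may test routinely. This stands as a limit: the finding concerns the protocol text, not what the site does. It does not remove the point, because the overview's discretionary wording would still need aligning with any mandatory test set elsewhere.

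**The quoted sentence is a visit procedure, not the entry rule.** No exclusion in 3.1b has a verification method, and an unconditional exclusion already obliges the investigator to establish pregnancy status. It is right that the two provisions do not contradict each other and that an investigator may test everyone. But permission is not a requirement. The sentence covers each research visit, including baseline, and is the only testing rule given.

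**Standard care covers it.** That statement in 3.6 concerns treatment of the relapse. The same section says the research scans are not diagnostic, so it does not extend to research contrast.

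**Contrast may have been given already.** Section 3.1a requires an enhancing lesion for entry, so a contrast scan must precede or establish eligibility. This also stands: the baseline research scan cannot be assumed to be the patient's first contrast exposure. It does not dispose of the drug exposure, or of a further contrast scan where an earlier clinical one was done.

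**Conclusion.** The point holds as a gap in a participant-safety safeguard. Under the testing rule as written, an unsuspected pregnancy could go undetected before the first ACTHAR dose and the baseline research contrast MRI. The chance of this among 18 patients cannot be calculated from the documents, and inference is unaffected. The conclusion assumes that no mandatory test is set out in the consent pages or local procedures. If one is, the remaining work is to align the wording.

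Three stronger readings are tempting, but the documents do not support them.

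- *The protocol contradicts itself, or pregnant patients will be enrolled.* The exclusion is unconditional and testing everyone is allowed. What is missing is a requirement.
- *A pregnancy found after dosing would cost 1/18 = 5.6% of the patients.* This holds only if the patient leaves before any later MRI. Section 3.1a keeps anyone with one dose, a baseline MRI and one further MRI. Section 3.5 retains data already collected, and the mixed model in 3.4 can use partial follow-up.
- *Exclusion 5 requires tests throughout follow-up.* It governs entry. Conception during follow-up does not breach it, so later tests are a matter of choice.

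**What to change.** In the opening study overview, replace the discretionary pregnancy-test wording with: *A urine pregnancy test will be done in all women of childbearing potential, and a negative result is required before the baseline research contrast MRI and before the first ACTHAR dose.* Add the same check beside the renal function check in section 3.6. If the baseline scan also serves to establish the enhancing lesion for eligibility, the test must come before that scan. Urine analysis for infection can stay discretionary, and exclusion 5 needs no change. If local procedure or the consent form already requires the test, state that instead.

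**Cost.** At most 18 entry urine tests. A same-visit result fits the 48-hour window. A patient who tests positive is excluded before dosing, and the schedule and analysis are unchanged.

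**Optional additions.** The test could be repeated before retreatment under 3.2 (one more per retreated woman) and before the four later scans (four more). The ceiling is then 1 + 1 + 4 = 6 per woman, or 18 × 6 = 108 in total. If contrast is withheld after a positive result, the Gd+ lesion, perfusion, Ktrans and post-contrast T1/T2 data for that visit are lost. Assuming contrast at all five scans, there are 18 × 5 = 90 patient-scans. One patient would then lose contrast data at 1/90 = 1.1% of them, up to 4/90 = 4.4% if contrast is withheld at all four later scans.

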1.1 Overview

Multiple sclerosis (MS) is a demyelinating disease of the CNS. In a vast majority of patients, its clinical course is characterized by transient attacks of acute neurological compromise, followed by variable degree of recovery. Each relapse leaves a patient with some degree of residual disability. Higher number and longer duration of relapses are associated with greater loss of function. Hence, it is imperative that these relapses are optimally treated and curtailed in duration to allow for maximal recovery and repair.

ACTH (ACTHAR or IV formulation) has long been used for the treatment of MS relapses ^{1, 2}. ACTH has equivalent efficacy to high-dose IV methyprednisolone in curtailing the duration of MS relapses ^{3, 4}. ACTH has an advantage over steroids in that it has a short half-life and much less deleterious steroidogenic effect on bone and fat metabolism ⁵. Importantly, ACTH has a unique mechanism of action on immune and brain cells through melanocortin receptors (MCRs), which promote production of regulatory and anti-inflammatory cytokines and support oligodendrocyte precursors and neuronal function, all of which could lead to better repair of MS lesions and favorable clinical outcome ⁶.

Several studies have shown beneficial effects of ACTHAR on clinical relapses ⁷. However, there is little *if any* knowledge about the benefits of ACTHAR in suppressing inflammatory lesion activity and enhancing remyelination over time as assessed by MRI. Improvement in the inflammatory activity, and particularly repair, in MS lesions leads to

improved clinical outcome and less residual clinical deficit. Often during the MS course, the ratio of new MRI disease activity to clinical relapses can be 10:1. Hence, suppression of this MRI activity is relavant to clinical outcome.

The studies proposed herein will provide a better understanding of the effects of ACTHAR in improving MRI lesion characteristics over time. The complementary immune and genetic studies will further provide evidence for the mechanism of action (MOA) of ACTHAR in improving immune dysfunction related to MS relapse. This is a one of a kind study, involving both advanced/state-of-the art MRI techniques and immune studies to assess the beneficial effects of ACTHAR in MS relapses in the same patients over time.

1.2 Hypothesis: ACTHAR during acute attacks will reduce inflammation and promote CNS repair as assessed by conventional and advanced MRI techniques and it will shift the inflammatory immune response associated with a MS relapses towards a more regulatory and nurturing immune response.

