- 1. **Aim1**. Determine immune subset expression in CD4+FOXP3 Tregs and CD8+CD28- T suppressor cells by flow cytometry at each visit above.
- 2. **Aim 2**. Determine global gene expression profiling in MNC with 913,000 probes at each visit above. Bioinformatics will include pathway analysis and ACTHAR-induced RNA signature.
- 3. **Aim 3**. Determine serum protein profiling for immune-regulated cytokines (Th1, Th2, Th17, monokines...) and neuroprotective proteins (NGF, BDNF, ACTH, HGF, CNTF, IL-10...) at each visit above.

4. **Aim 4.** All data from protein and gene expression, as well as immune subset expression will be compared to our database generated from therapy-naïve stable and exacerbating MS. ACTHAR signature will analyzed based on these comparisons.

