2.5 Methods

Blood is drawn from 18 MS patients at baseline, last day of ACTHAR (day 10 of therapy), 1 month post 1st dose, and months 3 and 6. Mononuclear cells (MNCs) from four 8cc heparin green-top tubes (40-60 million cells) are separated on Ficoll-Paque gradients. 30M cells are needed for flow cytometry. 20M cells are needed for total RNA preparation.

Specific Aim 1. Determination of ACTHAR effects on immune cell subsets in relapsing remitting MS (RRMS), emphasizing expression on CD8 cells including the CD8+CD28-regulatory subset. Flow cytometry will be conducted to determine the effect of ACTHAR on in vivo expression of surface markers on T cells (CD4, CD8, CD28, FOXP3). Reagents are from e-Biosciences and B-D. (MAbs = CD4, CD8, CD28, CD27, CD25, FOXP3).

Specific Aim 2. Global gene expression profiling in MNC will be measured with 913,000 probes at each sample. Bioinformatics will include pathway analysis and ACTHAR-induced RNA signature. Total RNA will be isolated from 20M cells, as the template for synthesizing cDNA for gene expression array analysis with Affy HTA kit. RT-PCR will be performed for validation of specific gene signatures.

Specific Aim 3. Serum from each sample will be applied on Procarta multiplex assay plates according to manufacturer's instruction. Immune, neuroprotection, and other proteins will be measured with 40 highly-selected targeted antibodies for Th1, Th2, Th17, monocyte, neuroprotection, cell proliferation and death, and adhesion molecule panels.

Specific Aim 4. Advanced bioinformatics with Gene Set Variation Analysis:

- 1. Identify differential gene expression (DEG) between groups;
- 2. Analyze pathways by Ingenuity Pathway Analysis (IPA);
- 3. Discover transcriptional signature of genes and gene pathways;

4. Build a predictive model using machine learning algorithms including Random Forests (RFs) and Support Vector Machines (SVMs).

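### The immune studies aim at ACTHAR's mechanism, but nothing planned distinguishes a steroid-mediated change from a direct melanocortin effect, and the day-10 sample is not tied to injection time

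*Combined protocol and SAP*

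**What the plan says.** **Purpose.** Section 1.1 states: "The complementary immune and genetic studies will further provide evidence for the mechanism of action (MOA) of ACTHAR in improving immune dysfunction". Section 2.6 repeats, more cautiously, that the data may improve understanding of the mechanism.

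**Routes named.** Section 1.1 says "ACTH has a unique mechanism of action on immune and brain cells through melanocortin receptors (MCRs"). Just before that, it compares ACTH with steroids and refers to a "much less deleterious steroidogenic effect on bone and fat metabolism". The steroid effect is called less harmful, not absent. Section 2.1 adds other actions, including NF-κB inhibition, sympathetic activation and more IL-10.

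**Measurements.** Section 2.4, Aim 3 lists "neuroprotective proteins (NGF, BDNF, ACTH, HGF, CNTF, IL-10...) at each visit above". Section 2.5 describes the serum panel as "40 highly-selected targeted antibodies for Th1, Th2, Th17, monocyte, neuroprotection, cell proliferation and death, and adhesion molecule panels". Gene expression is genome-wide (913,000 probes), with pathway analysis and gene set variation analysis (GSVA). Aim 4 derives the signature by comparison with a database of therapy-naïve stable and exacerbating MS.

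**Timing.** After baseline, blood is drawn at "last day of ACTHAR (day 10 of therapy), 1 month post 1st dose, and months 3 and 6" (2.5). The first injection is given in clinic. For the rest, the opening overview says: "All subsequent injections will be self-administered by the patient".

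**The concern.** ACTH stimulates the adrenal gland to release cortisol, and cortisol itself alters circulating lymphocytes and gene expression. That is general pharmacology; the documents support it only through the word steroidogenic. If part of the observed change travels by that route, the plan has no means of showing it. The result would carry the ACTHAR label and could be read as support for the melanocortin account in 1.1.

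The plan already treats outside steroid exposure as relevant: 3.1b excludes patients given steroids in the 30 days before ACTHAR. It does not look at the steroid response that the study drug may itself produce.

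Timing matters for a related reason. Section 1.1 says ACTH has a short half-life, and Aim 3 measures ACTH at each visit. A day-10 level of a short-lived injected drug is hard to interpret without the hours since injection. The same holds for any marker that responds acutely to the dose.

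**Working it through.** **1. Is a route-separating measure or analysis specified?** The documents state no figure to reproduce here, so the check is by reading.

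| Item needed | What the documents give |
|---|---|
| Cortisol assay | None specified; the word does not appear. Aim 3 ends in an ellipsis and the 40 antibodies are not all named, so 'not specified' is the exact statement |
| Steroid-response gene set | None named for GSVA or pathway analysis (2.5) |
| Steroid-treated comparator | None; the database groups are therapy-naïve (2.4, Aim 4) |
| Relevant model or contrast | None in 3.4 |
| Injection time record | None |
| Clock time of blood draws | None |

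**2. Which samples does timing affect?** The planned course lasts 10 days, so of the five draws only day 10 is during treatment with earlier doses on board. The later draws fall after the planned course. Section 3.2 changes this for some patients: after 14 days it allows a second 10-day ACTH course or IV methylprednisolone, with blood draws continuing as scheduled. If the 14 days run from the first dose, a second course begun on day 15 would end on day 24 (15 + 9), shortly before the 1-month draw. A later start could overlap that draw.

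**3. How much could uncontrolled timing cost? (illustration)** Assume a fraction p of patients is drawn after that day's injection, an acute shift e in the marker, and a usual SD of 25%. None of these is in the documents.

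- Mean shift = p × e.
- Variance ratio = [25² + e² × p(1 − p)] / 25².
- Information lost = 1 − 1/ratio.

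| p | e | Mean shift | Variance ratio | Information lost |
|---|---|---|---|---|
| 0.5 | 20% | 10% | (625 + 100)/625 = 1.16 | 14% |
| 0.5 | 40% | 20% | (625 + 400)/625 = 1.64 | 39% |
| 0.1 | 20% | 2% | (625 + 36)/625 = 1.06 | 5% |
| 0.1 | 40% | 4% | (625 + 144)/625 = 1.23 | 19% |

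The value p = 0.5 maximises p(1 − p), so the first two rows are the worst case for each e. The mean shift is bias only against a defined target, such as the pre-dose level, and the plan defines none.

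**4. Would measuring cortisol settle the matter?** Take a Pearson correlation (the method in 3.4) between day-10 cortisol and a marker, with two-sided alpha 0.05, 80% power and the Fisher z approximation. The smallest detectable |r| is tanh[(1.960 + 0.842)/√(n − 3)].

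- n = 18: tanh(2.802/3.873) = 0.62
- n = 15: tanh(2.802/3.464) = 0.67
- n = 12: tanh(2.802/3) = 0.73

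At n = 18, power is about 57% for r = 0.5, and an observed r of 0.5 has a 95% CI of about 0.04 to 0.78. Cortisol would therefore inform the picture without resolving it.

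**The case against.** The strongest reply is that the operative aims concern total effect. The hypotheses in 1.2 and 2.2, the objective in 2.3 and Aims 1 to 4 describe shifts in cell subsets, genes and proteins. None sets melanocortin against steroid routes, and 2.6 promises only better understanding. On that reading, a sentence limiting the mechanism claim would be enough. This stands in part: it is why total-effect results are unaffected and why the wording change in 2.6 carries much of the fix. It does not remove the mechanism goal that 1.1 and 2.6 both state.

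A reader might also infer several stronger things that the documents do not support:

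- *That a cortisol response would be reported as specific to ACTHAR.* The plan's labels are ACTHAR-induced and ACTHAR signature. A steroid-mediated change is still induced by ACTHAR.
- *That day 10 does mix patients before and after a dose, because injections are at home.* The text says self-administered and names no place. Patients might all inject at or after the visit. The point is that the plan neither fixes nor records it.
- *That separation is impossible.* The genome-wide data already planned hold relevant information, and pathway analysis might bring it out. What is missing is pre-specification.
- *That adjusting for cortisol would isolate the non-steroid route.* Cortisol here is a post-treatment mediator. With 18 patients in one group, the remainder after adjustment does not identify a direct effect.

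**Conclusion.** The concern holds in limited form. As written, the plan cannot distinguish a steroid-mediated change from a direct melanocortin effect, and the day-10 sample cannot be related to dosing. Estimation of the overall change under ACTHAR is not affected by this point; the limits that a single-group design puts on that estimate are a separate matter.

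The steroid contribution cannot be sized from the documents. The 5% to 39% information loss at day 10 rests wholly on the assumed split, shift and SD, and is not evidence of a loss in this trial. The conclusion rests on two premises: that ACTH can raise cortisol enough to affect immune markers (general pharmacology, hinted at in 1.1), and that no steroid assay hides behind the open-ended Aim 3 list. The change should be made, because it is nearly free and because injection and draw times cannot be recovered afterwards.

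**What to change.** In 2.4 and 2.5:

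1. Record the clock time of every injection and every blood draw. Keep each patient's draws in a similar clock window where feasible; the 48-hour start may constrain baseline. Report or adjust day-10 results by hours since the last injection.
2. Name a glucocorticoid-response gene set, with its source and version, before the expression data are examined. Score it in the planned GSVA, and report the ACTHAR signature with and without those genes, as a descriptive analysis.
3. Optionally, assay cortisol in the serum already drawn (up to 18 × 5 = 90 samples) as a descriptive marker. Flag samples taken after the retreatment or IV methylprednisolone that 3.2 allows; a cortisol value is not a measure of methylprednisolone exposure.

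In 2.6, state that the signature is the total effect of ACTHAR including any steroid-mediated part, and that what the steroid set does not explain is only suggestive of a non-steroid route. Align the sentence in 1.1 with this.

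The cost is a small log, some extra analysis, one assay if the option is taken, and a narrower mechanism claim. Dosing, visits and sample size do not change.
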